Outcome measures obtained after using the Revo-M foot for 8 weeks will be compared to baseline measures obtained using everyday feet with a 2-sided Wilcoxon matched pairs signed ranks test. The Hochberg method will be used to adjust alpha for the multiple primary effectiveness endpoints, thereby limiting the family-wise alpha to 0.05. In this method, p-values are ranked from highest to lowest for each primary endpoint tested. If the highest p-value is ≤ 0.05 , all null hypotheses will be rejected and no further adjustment will be made. If, however, the highest p-value is > 0.05 , alpha will be adjusted to 0.025 (alpha/2). The remaining p-value must be ≤ 0.025 in order to be statistically significant. Adjustment of alpha will continue in this manner for all primary effectiveness endpoints. Two-tailed p-values \leq the Hochberg adjusted alpha will indicate statistical significance. Primary efficacy endpoints (2 endpoints) will be considered one family and secondary efficacy endpoints (3 endpoints) will be considered a second separate family. The Hochberg method will not be applied to exploratory endpoints.

If the observed p-value is \leq the Hochberg adjusted critical value, the difference will be regarded as statistically significant. Because this is a randomized crossover study, the Revo-M may be either the first or second new foot used after baseline measures with the everyday feet. It is important to assess whether differences between Revo-M and everyday feet scores are influenced by the order in which the new feet are assigned. To evaluate this a difference score will be computed by subtracting everyday feet scores from Revo-M scores. Difference scores for subjects receiving the Revo-M foot first will be compared to those of subjects who received the Revo-M foot second (after a comparative foot) using Wilcoxon's rank sum test. A resulting p-value ≤ 0.05 will indicate that differences in the specified outcome measure may depend on the order in which the Revo-M was

assigned and not simply due to the Revo-M itself. Interpretation of differences between Revo-M and everyday feet scores will be modified accordingly.

Primary Efficacy Endpoints

Primary Efficacy Endpoint #1: Perception of mobility as measured by the PLUS-M. It is hypothesized that PLUS-M scores will be higher for subjects when they are using the Revo-M compared to their everyday feet. In statistical terms the null and alternative hypotheses are as follows:

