$$H_0: \mu_{\text{Revo-M}} \leq \mu_{\text{Everyday}}$$

$$H_A: \mu_{\text{Revo-M}} > \mu_{\text{Everyday}}$$

Where H_0 is the null hypothesis, $\mu_{\text{Revo-M}}$ is the mean PLUS-M score using the Revo-M, μ_{Everyday} is the mean PLUS-M score using the everyday feet and H_A is the alternative hypothesis indicating that perception of mobility as measured by the PLUS-M is greater for Revo-M than for everyday feet.

The hypothesis will be tested using a 2-sided Wilcoxon matched pairs signed ranks test. If the observed p-value is \leq the Hochberg adjusted critical value and the mean of PLUS-M scores using the Revo-M foot is greater than PLUS-M scores using the everyday feet, the null hypothesis will be rejected in favor of the alternative hypothesis and the superiority of the Revo-M will be supported.

Primary Efficacy Endpoint #2: Level of activity restrictions as measured by the Trinity Amputation and Prosthesis Experience Scales Activity Restrictions subscale (TAPES-AR). It is hypothesized that TAPES-AR scores will be lower for subjects when they are using the Revo-M compared to their everyday feet. In statistical terms the null and alternative hypotheses are as follows:

$$H_0: \mu_{\text{Revo-M}} \geq \mu_{\text{Everyday}}$$

$$H_A: \mu_{\text{Revo-M}} < \mu_{\text{Everyday}}$$

Where H_0 is the null hypothesis, $\mu_{\text{Revo-M}}$ is the mean TAPES-AR score using the Revo-M, μ_{Everyday} is the mean TAPES-AR score using the everyday feet and H_A is the alternative hypothesis indicating that level of activity restrictions as measured by the TAPES-AR is less for Revo-M than for everyday feet.

The hypothesis will be tested using a 2-sided Wilcoxon matched pairs signed ranks test. If the observed p-value is \leq the Hochberg adjusted critical value and the mean of TAPES-AR scores using the Revo-M foot is less than TAPES-AR scores using the everyday feet, the null hypothesis will be rejected in favor of the alternative hypothesis and the superiority of the Revo-M will be supported.

Secondary Efficacy Endpoints

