Secondary Efficacy Endpoint #1: Level of walking endurance as measured by the distance walked in the six-minute walk test (6MWT) and the perceived exertion (RPE) measured by Borg CR100. No hypothesis will be tested. Instead, the percentage of subjects (along with the exact 95% binomial confidence interval) with either a clinically meaningful improvement in the distance walked in the six minute walk test or a clinically meaningful decrease in the rating of perceived exertion (RPE) while wearing the Revo-M foot compared to the everyday foot will be computed. A clinically-significant improvement in the 6MWT is defined as a change in distance of greater than 45 meters [Resnik 2011]. A clinically-significant improvement in the RPE is defined as a change greater than 10 points [Ries 2005].

Secondary Efficacy Endpoint #2: Perception of balance confidence as measured by the extended Activities-specific Balance Confidence (ABC) Scale. It is hypothesized that ABC scores will be higher for subjects when they are using the Revo-M compared to their everyday feet. In statistical terms the null and alternative hypotheses are as follows:

$$H_0: \mu_{\text{Revo-M}} \leq \mu_{\text{Everyday}}$$

$$H_A: \mu_{\text{Revo-M}} > \mu_{\text{Everyday}}$$

Where H_0 is the null hypothesis, $\mu_{\text{Revo-M}}$ is the mean ABC score using the Revo-M, μ_{Everyday} is the mean ABC score using the everyday feet and H_A is the alternative hypothesis indicating that balance confidence as measured by the ABC scale is greater for Revo-M than for everyday feet.

The hypothesis will be tested using a 2-sided Wilcoxon matched pairs signed ranks test. If the observed p-value is \leq the Hochberg adjusted critical value and the mean of PLUS-M scores using the Revo-M foot is greater than PLUS-M scores using the everyday feet, the null hypothesis will be rejected in favor of the alternative hypothesis and the superiority of the Revo-M will be supported.

Secondary Efficacy Endpoint #3: Level of functional satisfaction as measured by the TAPES Functional Satisfaction (TAPES-FUN) subscale. It is hypothesized that TAPES-FUN scores will be higher for subjects when they are using the Revo-M compared to their everyday feet. In statistical terms the null and alternative hypotheses are as follows:

$$H_0: \mu_{\text{Revo-M}} \leq \mu_{\text{Everyday}}$$

$$H_A: \mu_{\text{Revo-M}} > \mu_{\text{Everyday}}$$

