Where H_0 is the null hypothesis, $\mu_{\text{Revo-M}}$ is the mean TAPES-FUN score using the Revo-M, μ_{Everyday} is the mean TAPES-FUN score using the everyday feet and H_A is the alternative hypothesis indicating that level of functional satisfaction as measured by the TAPES-FUN subscale is greater for Revo-M than for everyday feet.

The hypothesis will be tested using a 2-sided Wilcoxon matched pairs signed ranks test. If the observed p-value is \leq the Hochberg adjusted critical value and the mean of TAPES-FUN scores using the Revo-M foot is greater than TAPES-FUN scores using the everyday feet, the null hypothesis will be rejected in favor of the alternative hypothesis and the superiority of the Revo-M will be supported.

Exploratory Efficacy Endpoints

Although hypotheses have not been specified, statistical testing will be done using Wilcoxon's matched pairs signed ranks test comparing Revo-M to both comparative devices, the Taleo and the ProFlex, and comparing the Revo-M to the everyday foot (baseline at the end of Period I and crossover at the end of Period IV). However, as these objectives are exploratory in nature, any statistically significant differences will be considered to be hypothesis generating and not definitive. These results may be used to guide future studies with prosthetic feet.

Time Period

Data collection for all subjects will be collected from the time of enrollment until the end of Period IV. Patients may be given the opportunity to continue in Phase V for continued follow-up with the Revo-M for an additional 6 months.

Data Analysis

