Data analysis will be primarily descriptive in nature. Categorical variables (such as gender) and ordinal variables (such as severity of adverse events) will be summarized by absolute and relative (percentages) frequencies. Continuous variables (such as age) will be summarized by the mean, median, standard deviation, minimum and maximum values observed. In addition, change in continuous measures of effectiveness (such as PLUS-M scores) will be evaluated by subtracting baseline from follow-up scores. The mean, median, standard deviation, minimum and maximum values observed will be used to summarize change scores. In addition, the significance of differences between baseline and follow-up scores may be tested using Wilcoxon's matched pairs signed ranks test. Two-tailed p-values ≤ 0.05 will indicate statistical significance. Each variable will be analyzed separately. For each variable analyzed, only subjects with valid values will be included in the analysis. A subject need not have valid values on all variables to be included in the analysis of any given variable.

Risk-Benefit Analysis

The potential risks and benefits of the Revo-M as well as the comparative devices, Taleo and ProFlex XC, are identified in the Instructions for Use.

Risks and Minimization of Risks

The Revo-M devices to be assessed in this study will have undergone thorough verification testing. The risk analysis for the Revo-M prosthetic foot resulted in a list of known or expected risks as shown in the table below. All were deemed "As Low As Reasonably Possible."

Risk	Potential harm		
	Injury	Function lost	Health hazard
Damage/ Break of load bearing parts	X		
Break of functionally relevant parts	X		
Failure of the guide elements for the tension element	X	X	
The connection to the prosthesis is lost	X		
Foot twists	X		
Damage to the product during manufacture or use	X		
Incorrect alignment	X		
Not compliance with the assembly guidelines	X		
Mechanical damage	X		
Mechanical damage of load bearing parts	X	X	

Risk	Potential harm		
	Injury	Function lost	Health hazard
Use not according to the MOBIS classification	X		
Use without foot cover	X		
Overload of the prosthesis caused by unsuitable combination of prosthetic components	X		
Weight limit is not specified or not readable	X		
Safety instructions are not sufficiently described			X
Use on more than one user	X	X	
Product is used too long	X		
Exceeding the time-stability of supporting structures	X		

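### The superiority rule for Secondary Endpoint #2 (ABC) tests the direction of PLUS-M, so nothing in the rule requires ABC to have improved

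*Combined protocol and SAP*

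**What the plan says.** In the combined protocol and SAP, the paragraph on Secondary Efficacy Endpoint #2 is about ABC up to its last sentence. It opens with "It is hypothesized that ABC scores will be higher for subjects when they are using the Revo-M compared to their everyday feet". Both hypotheses are written on the mean ABC score, and the alternative is explained as meaning that "balance confidence as measured by the ABC scale is greater for Revo-M than for everyday feet". The test is a two-sided Wilcoxon signed-rank test at a Hochberg-adjusted critical value.

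The decision sentence then asks for two things: a p-value at or below the critical value, and that "the mean of PLUS-M scores using the Revo-M foot is greater than PLUS-M scores using the everyday feet". If both are met, the null hypothesis is rejected and superiority of Revo-M is supported. ABC does not appear in that condition. The same words stand, correctly, in the rule for Primary Efficacy Endpoint #1, which is PLUS-M.

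The other two tested endpoints check their own scale:
- Primary Efficacy Endpoint #2: "the mean of TAPES-AR scores using the Revo-M foot is less than TAPES-AR scores using the everyday feet"
- Secondary Efficacy Endpoint #3: "the mean of TAPES-FUN scores using the Revo-M foot is greater than TAPES-FUN scores using the everyday feet"

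**The concern.** A two-sided p-value says that ABC differs between feet but not which foot is better. The plan relies on the added mean condition to turn significance into superiority. For ABC that condition refers to another questionnaire, so the rule can go wrong in two ways:

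- **False claim.** ABC is significantly lower on Revo-M and mean PLUS-M is higher by any amount. The rule supports superiority on balance confidence.
- **Missed gain.** ABC is significantly higher on Revo-M and mean PLUS-M is equal or lower. The rule does not support superiority.

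The two scales could diverge on the protocol's own account. The Background and Rationale says that the elasticity of this class of foot can work against stability, and the ABC description adds five items to study balance confidence with this foot. The section on interim analysis and adaptive design also foresees a pivotal trial that covers the secondary objectives and uses the feasibility subjects' data. An uncorrected rule could be carried into it.

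**Working it through.** **1. The four decision rules side by side**

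| Endpoint | Scale in the hypotheses | Scale in the direction condition |
|---|---|---|
| Primary #1 | PLUS-M | PLUS-M |
| Primary #2 | TAPES-AR | TAPES-AR |
| Secondary #2 | ABC | **PLUS-M** |
| Secondary #3 | TAPES-FUN | TAPES-FUN |

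No other section supplies an ABC condition. The Hypothesis section defines significance only. The Data Analysis section gives descriptive summaries and a general two-tailed threshold.

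**2. The plan's own figure, to fix the PLUS-M effect**

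Inputs from the Sample Size section: PLUS-M difference 5, SD 7.7, power 80%, alpha 0.05, N = 22; TAPES-AR difference 0.2, SD 0.3, N = 21. The method is a two-sided paired t-test sample size divided by the signed-rank relative efficiency 3/π, with the SD read as that of the paired differences.

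- PLUS-M: paired t gives 21; 21 ÷ (3/π) = 21.99, so 22, as stated.
- TAPES-AR: paired t gives 20; 20 ÷ (3/π) = 20.94, so 21, as stated.

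Simulating the exact signed-rank test gives 80.5% power at n = 22 and 80.0% at n = 21. So 7.7 can be treated as the SD of differences, and the planned PLUS-M effect is 5/7.7 = 0.649 SD.

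**3. What the written rule does**

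- Written rule: superiority if p(ABC) ≤ α and mean PLUS-M difference > 0.
- Corrected rule: superiority if p(ABC) ≤ α and mean ABC difference > 0.

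Take the stated minimum of n = 24. If the planned PLUS-M effect is real, the chance that the mean PLUS-M difference is positive is Φ(0.649 × √24) = Φ(3.18), about 0.999. The PLUS-M condition is then almost always met, and the written rule reduces to any significant ABC difference in either direction. If PLUS-M is truly unchanged and uncorrelated with ABC, the condition is a coin toss and the rate halves.

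**4. Simulation**

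Settings: exact two-sided signed-rank test on ABC, n = 24, normal paired differences, 200,000 runs per cell. The ABC effects and the ABC/PLUS-M correlations (0, 0.5, 0.8) are assumptions, because the documents give none. The critical value is 0.05, the largest that Hochberg allows. Where a range is shown, it spans the three correlations.

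| True ABC effect | True PLUS-M effect | Written rule | Corrected rule |
|---|---|---|---|
| 0.3 SD worse | +0.649 SD | 28% | under 0.1% |
| 0.5 SD worse | +0.649 SD | 63% | under 0.1% |
| none | +0.649 SD | 4.8–5.0% | 2.4–2.5% |
| 0.3 SD worse | none | 3–14% | under 0.1% |
| 0.5 SD worse | none | 19–31% | under 0.1% |
| 0.5 SD better | none | 32–44% | 63% |

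At smaller critical values, with the planned PLUS-M effect, the written-rule rates are:
- ABC 0.3 SD worse: 19% at 0.025 and 15% at 0.0167.
- ABC 0.5 SD worse: 51% at 0.025 and 44% at 0.0167.

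The halving in step 3 can be seen at correlation 0: 0.278 ÷ 2 = 0.139 and 0.628 ÷ 2 = 0.314, against simulated 0.139 and 0.315.

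A separate run (40,000 per cell, correlations 0 to 0.9) agrees and adds two cases:
- Neither scale truly changes: both rules declare superiority in about 2.5% of trials. At correlation 0, about half of the written rule's declarations have ABC worse (1.29% of 2.65%).
- ABC 0.5 SD better with the planned PLUS-M gain: both rules give about 63% and differ by less than 0.1 percentage point.

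**The case against.** The best defence is that this is a drafting slip which the paragraph itself resolves. The hypotheses name ABC, the rule ends by rejecting in favour of that alternative, the parallel rules use their own scales, and the Data Analysis section says "Each variable will be analyzed separately". Reported change scores would expose a wrong-direction result. The 28% and 63% need ABC truly worse, PLUS-M truly better by the full planned amount, and an analyst who follows the sentence against the data. The study is a feasibility study with a mainly descriptive analysis, and its interim decision and progression turn on the primary objectives.

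Most of this stands. The intent is not in doubt, and the rates are illustrations that matter only when the two scales move apart. If PLUS-M is unchanged and the correlation is 0.9, the rate for ABC 0.3 SD worse falls to 1.6%.

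It does not rescue the rule. Descriptive tables would reveal the conflict but would not alter what was pre-specified, and someone would have to reinterpret the rule after seeing the data. The sentence on separate analysis supports the correction, because the written rule makes the ABC conclusion depend on PLUS-M. Since subjects enter each analysis on valid values for that variable, the PLUS-M mean could even come from a different set of subjects than the ABC test.

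**Conclusion.** The concern holds. The decision rule for Secondary Endpoint #2 is wrong as written and should be fixed. It never asks whether ABC improved, and no other text supplies that check.

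The practical size depends on how often ABC and PLUS-M move in opposite directions, which the documents do not quantify. Under the stated assumptions, a true ABC worsening of 0.3 to 0.5 SD alongside the planned PLUS-M gain would be declared superiority in 28% to 63% of trials at 0.05, against under 0.1% when corrected. A true ABC gain of 0.5 SD with PLUS-M unchanged would be recognised in 32–44% instead of 63%. Where both scales improve, as the sponsor expects, the error has almost no effect.

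The primary endpoints, their Hochberg family and the sample sizes of 22 and 21 are untouched.

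**What to change.** In the decision sentence of Secondary Efficacy Endpoint #2, replace PLUS-M with ABC at both places. The condition then requires mean ABC on Revo-M to exceed mean ABC on the everyday feet, which matches the stated alternative and the other three rules. No sample size, alpha level, visit or procedure changes.

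A separate, minor clarification can be made in the same edit. The Hypothesis section says "secondary efficacy endpoints (3 endpoints) will be considered a second separate family", while Secondary Endpoint #1 says "No hypothesis will be tested". State that the secondary Hochberg family is the two tested endpoints, ABC and TAPES-FUN (0.05, then 0.025), and that the walk-test and exertion endpoint is descriptive. Counting an untested third endpoint (0.025, then 0.0167) would only be conservative: with two independent true nulls, family-wise error is 0.033 instead of 0.050.

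The cost is one sentence corrected and one clarified.

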The study is planned to be divided into four periods as illustrated in Figure 4. The only clinical measures to occur from the beginning of Period I are the StepWatch, Patient Journal, and Socket Comfort Score. After enrollment, the subject will spend 8 weeks (+/-2 weeks) using their own energy storage and return foot. Informed consent, demographic information, general health information, and adverse events will be collected during this period. After enrollment, the subject will be randomized to Revo, Taleo (if a transfemoral amputee), or the Proflex XC (if a transtibial amputee).

Period II – Period IV

Baseline measures are taken just prior to Period II. After the first 8 week follow up, the subject will crossover to the second comparator. After the second 8 week follow up, the subject will crossover to control. During Period IV, assessments will be repeated as in baseline. Table 2 summarizes the assessments and order of events.

[figure not shown]

Figure 4 Study Periods and Visits

Table 2 Assessments by Period and Study Visit

Period I (Control)			Period II (Revo/ Comparative)	Period III (Revo/ Comparative)	Period IV (Control)
	Visit 1	Visit 2	Visit 3	Visit 4	Visit 5
Measurement	Enrollment	Baseline 8 ± 2 weeks	Period II Follow up 8 ± 2 weeks	Period III Follow up 8 ± 2 weeks	Period IV Follow up 8 ± 2 weeks
Demographics / General Health	X				
SCS	X	X	X	X	X
ABC (extended)		X	X	X	X
PLUS-M		X	X	X	X
PROMIS-F (7a)		X	X	X	X
TAPES-FUN + TAPES-AR		X	X	X	X
EQ-5D-5L		X	X	X	X
6 Minute Walk Test (incl. BORG RPE and continuous HR)		X	X	X	X
Foot Preference Questionnaire					X
Patient Journal (incl. Pain Interference)	X	X	X	X	X
Step Count*	X	X	X	X	X
Adverse Events	X	X	X	X	X
Fitting with prosthetic foot for subsequent Period		X	X	X	

* Subject is fitted with StepWatch at previous visit so that the data may be collected prior to the following visit, this process starts at enrollment

Objectives

Safety

Safety Objectives

1. To characterize all device-related adverse events, stumbles, and falls experienced by subjects in the study by frequency and severity.

Effectiveness

Primary Efficacy Objectives

1. To characterize perception of mobility as measured by the PLUS-M while wearing the Revo-M compared to the everyday feet.
2. To characterize the level of activity restrictions as measured by the Trinity Amputation and Prosthesis Experience Scales Activity Restrictions subscale (TAPES-AR) while wearing the Revo-M compared to the everyday feet.

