The fittings during Period II and Period III are determined at random and according to amputation level. Subjects will be randomized to start with either the Revo (regardless of amputation level) or the comparative foot: Taleo if TF or KD, Proflex XC if TT. After completing Period II with the assigned foot, subjects will cross over to be fit with either the Revo, if starting with the comparative foot or the comparative foot if starting with the Revo.

Fitting process for the Revo-M investigational foot

The Revo prosthetic foot has several components which have different mechanical characteristics to allow the foot to be tailored to the patient. Subjects will complete several walking trials to determine the optimal configuration.

Fitting process for the comparative feet: Taleo and ProFlex XC

The Taleo is customizable with heel wedges that come in three different stiffnesses (soft, medium and hard). The CPO may give the subjects the opportunity to try each wedge to determine which is best.

ProFlex XC does not have any customizable components, so no configuration process is required.

Home-use Periods

Subjects will have four home-use periods during the study approximately 8 weeks in duration as shown in Figure 4 above. Prior to each home-use period, subjects will be fitted with the assigned foot and be given a Patient Journal and a StepWatch activity monitor. The Patient Journals will be completed weekly for the duration of the home-use period. The StepWatch will be worn for approximately one month and then mailed back to the clinical site. At the end of the home-use period, subjects will return to the site for a follow-up visit for assessments (see Clinical Tests & Measures for test descriptions).

Clinical Tests & Measures

Data collection for the following clinical functional assessments will be collected on eCRFs. Several questionnaires and two performance based measures will be used in the study.

For an overview of the assessments required by visit, see Table 2.

Activity monitoring (daily step counts)

The StepWatch will be used for activity monitoring to collect daily step counts during the first month of each home-use period.

Six-minute walk test (6minWT)

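### The test of Revo-M against the comparative foot, the trial's only randomized contrast, ignores period: it loses precision if there is a period effect, and the estimate shifts if the two sequences turn out unequal

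*Combined protocol and SAP*

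**What the plan says.** All references are to the combined protocol and SAP.

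- **Design (Study Summary; Randomization).** The everyday foot has fixed positions. It comes first ("After enrollment, the subject will spend 8 weeks (+/-2 weeks) using their own energy storage and return foot") and last ("After the second 8 week follow up, the subject will crossover to control"). Only the middle two periods are randomized: "The fittings during Period II and Period III are determined at random and according to amputation level", and "Subjects will be randomized to start with either the Revo (regardless of amputation level) or the comparative foot". Transfemoral and knee-disarticulation subjects get the Taleo, transtibial subjects the ProFlex XC. No allocation ratio or blocking is stated.
- **Analysis of this contrast (Exploratory Efficacy Endpoints).** The plan specifies a Wilcoxon "matched pairs signed ranks test comparing Revo-M to both comparative devices, the Taleo and the ProFlex". No period or sequence term appears there or elsewhere. The same section calls the results hypothesis generating.
- **Order check (Hypothesis).** For Revo-M against everyday feet, "a difference score will be computed by subtracting everyday feet scores from Revo-M scores", and then "Difference scores for subjects receiving the Revo-M foot first will be compared to those of subjects who received the Revo-M foot second". A small p-value changes the interpretation of that contrast. It adjusts no estimate, and the contrast with the comparative foot is not mentioned.
- **Missing data (Data Analysis).** Each variable uses the subjects who have valid values, so the sequence split can differ by endpoint.

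**The concern.** Periods II and III form a two-sequence, two-period crossover of Revo-M and one comparative foot. Any general change between those periods, such as practice, season or repeated questionnaires, enters the Revo-M minus comparative difference with a minus sign when Revo-M comes first and a plus sign when it comes second. A signed-rank test on the pooled differences does not separate this from the treatment difference. With equal sequences the change cancels from the mean but widens the spread, so power is lost. With unequal sequences part of it stays in the estimate.

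This contrast is Exploratory Objective 1 and covers all primary and secondary outcome measures. It is also the only one whose treatment order is protected by randomization. The plan already treats order as a concern for the contrast with everyday feet.

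**Working it through.** **The plan's own figures first.** Sample Size gives 22 subjects for PLUS-M (difference 5, SD 7.7) and 21 for TAPES-AR (0.2, 0.3), for 80% power at alpha 0.05. A two-sided paired t-test needs 21 and 20. Dividing by the signed-rank efficiency 3/π gives 21 × π/3 = 21.99, so 22, and 20 × π/3 = 20.94, so 21. Both figures reproduce if the SDs are SDs of paired differences. They apply to Revo-M against everyday feet. The plan gives no power for Revo-M against the comparative foot.

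**Inputs.** From the documents: SD 7.7, difference 5, two-sided alpha 0.05, at least 24 subjects, at least 12 per amputation level. Assumed: the SD and difference carry over to this contrast; the Period III minus Period II effect, π, is 0 to 5 points; no carry-over. Splits below are Revo-M first : Revo-M second.

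**Formula.** With true difference τ, the Revo-M minus comparative difference has mean τ − π if Revo-M is first and τ + π if second. Given the split, the pooled mean is shifted by

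π × (n second − n first) / N.

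With π = 5 and τ = 5:

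- 15:9: 5 × (9 − 15)/24 = −1.25, estimate 3.75
- 9:15: 5 × (15 − 9)/24 = +1.25, estimate 6.25
- 8:4 in one amputation level: 5 × (4 − 8)/12 = −1.67, estimate 3.33

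At 12:12 the shift is zero, but the pooled SD rises from 7.7 to √(7.7² + 2.5²) = 8.1 for π = 2.5, and to √(7.7² + 5²) = 9.2 for π = 5.

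**Simulated power for τ = 5** (normal differences; separate runs agree to within about 2 points):

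| Split | π | Signed-rank (plan) | Period-adjusted rank-sum |
|---|---|---|---|
| 12:12 | 0 | 84% | 83% |
| 12:12 | 2.5 | 81% | 83% |
| 12:12 | 5 | 71% | 83% |
| 15:9 | 0 | 85% | 81% |
| 15:9 | 2.5 | 70% | 81% |
| 15:9 | 5 | 45% | 81% |
| 9:15 | 5 | 92% (estimate too high) | 81% |
| 6:6 | 0 | 49% | 47% |
| 6:6 | 2.5 | 45% | 47% |
| 6:6 | 5 | 33% | 47% |
| 8:4 | 0 | 50% | 45% |
| 9:3 | 0 | 50% | 34% |

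The 8:4 figure for the rank-sum uses exact p-values; the normal approximation gives about 35%. The rows with 12 subjects matter because naming both devices reads most naturally as two tests, one per amputation level.

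**False positives (τ = 0).** At 16:8 the signed-rank rate is 6.7% for π = 2.5 and about 10% for π = 5, against about 4.5% adjusted. At 12:12 the test is conservative: 3.8% and 1.9%.

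**Averaged over the randomization.** Under simple 1:1 allocation (an assumption) and τ = 0, each difference is an equal mixture centred at −π and +π. That is symmetric about zero, so the signed-rank test is valid. Simulation at N = 24 gives 5.0% for π of 0, 2.5 and 5, and a mean estimate of 5.0 for a true 5; at N = 12 the rate is 4.1% to 4.3%. Under the same allocation the probability of exact balance is 16% for 24 subjects and 23% for 12. A split of 16:8 or worse has probability 15%, and 8:4 or worse among 12 has 39%.

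**The case against.** - **Validity.** A reader might infer that the signed-rank test discards the randomization or has an inflated error rate in general. The documents do not support that. Random order keeps the test valid and unbiased on average under simple allocation, and blocking would make it conservative. The shift and the excess false positives arise only given an unequal realised split. Drop-out could produce one, but the documents give no sign that it would differ by sequence. This objection stands, and it limits the claim to lost precision in general and a shifted estimate after imbalance.
- **Size of the period effect.** Five points equals the whole difference that the trial is powered for, and nothing in the documents suggests a change that large in people who have used a prosthesis for at least a year. At 12:12 with 2.5 points the loss is only 1 to 2 points of power. This stands: the larger figures are the top of an assumed range. Zero is not assured either.
- **Cost of the remedy.** With no period effect, adjustment costs little when sequences are near equal but about 15 points at 9:3. This stands, and is why blocking belongs with the fix.
- **Carry-over.** No washout is described. Unequal carry-over would bias the adjusted estimate too, so the fix does not deal with it.
- **Status.** The contrast is exploratory and unpowered, and no decision rule rests on it. This lowers the priority but does not make the unadjusted test the better choice.

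**Conclusion.** The point holds in a limited form. The plan's test for its only randomized contrast omits period, and the order check does not cover that contrast. If a period effect exists, the general cost is precision: at 12:12, about 81% against 83% power for an effect of 2.5 points and 71% against 83% for 5. After an unequal split the estimate also shifts by the formula above, upwards or downwards.

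These sizes rest on an assumed period effect of 0 to 5 points, the PLUS-M SD of 7.7 carried over to this contrast, a true difference of 5 and no carry-over. A reader might extend the concern to the primary and secondary results. Those compare Revo-M with everyday feet and are not affected. This is a cheap improvement to an exploratory analysis.

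**What to change.** 1. For Revo-M against the comparative foot, compute Period II minus Period III for each subject and compare the two sequences by a Wilcoxon rank-sum test, with exact p-values in small groups. Do this within amputation level, or stratified by amputation level when pooled. The means are τ − π and −τ − π, so π cancels and the shift between sequences is 2τ. Report half the Hodges-Lehmann shift with a 95% confidence interval.
2. State the allocation ratio and randomize in permuted blocks within amputation level. If allocation has already begun, the analysis change alone still removes the period effect.
3. State that the analysis assumes equal carry-over.

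The cost is SAP wording and a few lines of code, with no new data. If there is truly no period effect, power falls by about 2 points at 12:12 (84.4% to 82.5%) or 6:6, about 4 to 5 points at 15:9 or 8:4, and about 15 points in a stratum split as badly as 9:3, which blocking makes unlikely.
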